9.1.4 Statistical Analysis

With respect to Prentice's original proposal [36] current consensus is that for surrogate validation a correlation-based approach can be applied, with estimation of correlation measures on a trial level and an individual patient level [51][52][53]. We will apply the correlation approach according to Buyse et al. [40] to investigate the validity of MRD assessed by MPFC as surrogate endpoint for the long-term time to event endpoints OS (primary endpoint), RFS, and EFS (secondary endpoints). Two levels of surrogacy will be considered. On an individual patient level we will assess how well the surrogate predicts the survival endpoint. This is done by evaluating the prognostic value of MRD assessed by MPFC for the survival endpoint after adjustment for treatment. We will use the R^2 measure of Schemper and Henderson as well as Brier Score to assess the predictive accuracy of MRD assessed by MPFC [54]. Within the trial-level evaluation an individual patient data (IPD) meta-analytical approach will be used to test if the treatment effect on MRD assessed by MPFC allows reliable prediction of the treatment effect on the survival endpoints. We consider logistic regression for the surrogate endpoint MRD assessed by MPFC to achieve odds ratios (OR) and the proportional hazards model of Cox for the survival endpoints resulting in per trial hazard ratios (HR) and an error-in-variables linear

regression model of the log transformed HRs on the log transformed ORs. The trial-level coefficient of determination R_T^2 is then used to quantify the strength of association between the treatment effects on MRD assessed by MPFC and on the survival endpoints at the trial level.

In addition the surrogate threshold effect (STE) [42] will be estimated as the minimum effect of MRD assessed by MPFC that predicts a statistically significant effect on EFS, RFS and OS.

In addition, exploratory analyses will be performed on

- MRD assessed by MPFC after consolidation as a surrogate for OS, EFS and RFS
- Correlation of MRD assessed by MPFC after induction therapy and after consolidation therapy with respect to applied postremission treatment

A detailed statistical analysis plan (SAP) will be finalized before database closure.

10 Quality assurance and monitoring

Quality within the randomized interventional studies is assured by central and by on-site monitoring according to German law. On-site monitoring is implemented via each randomized interventional clinical trial including source data verification. Quality of laboratory procedures and analyses is assured by a quality-management system in place and regular MRD conferences and cross validation described above (see 6.2).

11 Executive committee

Tasks and responsibilities:

The executive committee (EC) is a collaborative operative board for the PERDAM study. Its overall roles are to review the results and outcomes collected in the PERDAM database, to define, foster and lead all multiparty publications of the PERDAM database. It has to assure that investigators of all study sites contributing to the PERDAM study will be appropriately involved in writing committees and authorship of publications. For number of authors and order, number of patients per site and the specific contributions must be taken into account. Details of operation and the interfaces to the other parties involved will be defined in a separate manual. Members of the EC are all collaborators listed on signature page-I and – II.

12 Ethical and legal aspects

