9.1.3 Proposed sample size/Power calculations

For validation of MRD assessed by MPFC as surrogate endpoint for OS, it is critical that the effect of treatment on MRD assessed by MPFC is closely correlated with the effect of treatment on OS. In our previous work [43] evaluating EFS as a surrogate endpoint for OS in AML we were able to show in an individual-patient data approach of 1,811 patients from four randomized trials (AMLHD 98B [44] AMLSG 06-04, [45] AMLSG 07-04, [46] and AMLSG 12-09, [47]) with 7 independent treatment comparisons due to multiple therapeutic questions that although EFS is only moderately correlated with OS (Spearman's rho = 0.76, 95% CI: [0.73, 0.79]) the treatment effects on EFS were strongly correlated with treatment effects on OS (correlation coefficient R = 0.99, for log hazard ratios). A two-level modelling approach was used to estimate the association between EFS and OS, and between treatment effects on EFS and OS [48]. At the individual level, a bivariate (Hougaard-copula-based) survival model with Weibull marginal hazards was fitted to model the joint distribution of EFS and OS, and Spearman's rank correlation coefficient (rho) was used to quantify the association between the endpoints. At the trial-level, an error-in-variables linear regression model was fitted to the estimated treatment effects (Weibull-model-based log hazard ratios) on EFS and OS, taking into account the estimation error. The correlation coefficient (R) was used to quantify the strength of association between the treatment effects.

Study	Comparison	Control arm	Experimental arm	N
AMLSG 06-04	1	Valproic acid	Valproic acid	96
		All-trans-retinoic acid + Valproic acid		93
AMLSG 12-09	2	Standard Azacitidine prior/concurrent/after		36
	3	Standard Azacitidine after		103
AMLSG HD98B	4	Standard All-trans-retinoic acid		64
		All-trans-retinoic acid		128
AMLSG 07-04	5	Standard All-trans-retinoic acid		92
	6	Standard All-trans-retinoic acid		369
	7	Valproic acid All-trans-retinoic acid + Valproic acid		95
				91

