The figure illustrates the correlation of the treatment effects on EFS and OS from 7 independent treatment comparisons as outlined and numbered in the table on the left. In this example clearly a substantial treatment effect could be demonstrated in 4 of the 7 treatment comparisons. Based on this experience we also expect treatment effects in most of the trials being part of the application. The sample size of the proposed study is fixed by the limited number of randomized trials and the trial-individual sample size calculation. We assume that 1000 patients are eligible for MRD assessment by MPFC after induction/salvage therapy. Based on i) our previous experience showing a high correlation of treatment effects on EFS and OS ($R=0.99$ for log hazard ratios with lower 95% confidence limit of 0.85), ii) the compelling data available on the prognostic value of MRD assessed by MPFC [5][21][22][23][24][25][26][27] and iii) the growing body of evidence indicating efficacy of new drugs especially in combination with induction/salvage therapy and not or to a much lesser extend later on in the treatment course (consolidation, maintenance) [10][32][49][50] the primary hypothesis is that MRD assessment by MPFC after induction/salvage therapy is a good surrogate for OS defined by trial level correlation R_T of the treatment effects on MRD assessed by MPFC and OS with $R_T > 0.8$.

We aim to test the one-sided null hypothesis $H_0: R_T \leq 0.8$ against the alternative hypothesis $H_1: R_T > 0.8$ at a significance level of $\alpha = 2.5\%$. To this aim we will use an individual patient data (IPD) meta-analytic approach and focus on the coefficient of determination (R_T)² to quantify the strength of association between treatment effects on MRD assessed by MPFC (log odds ratios, derived by logistic regression models) and treatment effects on OS (log hazard ratios, using Cox regression models) at the trial level. Based on the given sample size of at least 1000 patients within the included randomized clinical trials and considering a true R_T of 0.9 the power to identify this effect will be larger than 85%.

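### Does the silence of section 9.1.4 on the error covariance of log OR and log HR bias the trial-level correlation R_T?

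*Combined protocol and SAP*

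**What the plan says.** Section 9.1.4 takes per-trial effects from "logistic regression for the surrogate endpoint MRD assessed by MPFC to achieve odds ratios (OR) and the proportional hazards model of Cox", the second of these applied to OS, RFS and EFS. It then fits an error-in-variables "regression model of the log transformed HRs on the log transformed ORs" and reads the trial-level coefficient of determination from that model. The framework is the meta-analytic correlation approach of reference [40], described as "a correlation-based approach can be applied, with estimation of correlation measures on a trial level and an individual patient level". The section ends with "A detailed statistical analysis plan (SAP) will be finalized before database closure".

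Section 9.1.3 sets the test: H0 is R_T at most 0.8, one-sided 2.5%, using individual patient data, with a planning value of 0.9. On size it states "We assume that 1000 patients are eligible for MRD assessment by MPFC after induction/salvage therapy", and it cites "the compelling data available on the prognostic value of MRD assessed by MPFC" in support of the hypothesis. It also describes the group's earlier work on EFS as a surrogate for OS. There, a bivariate "survival model with Weibull marginal hazards was fitted to model the joint distribution of EFS and OS", and the trial-level regression used "treatment effects (Weibull-model-based log hazard ratios) on EFS and OS, taking into account the estimation error".

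No passage says how the covariance between the errors of log OR and log HR is obtained in PERDAM, and none says that it is left out.

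**The concern.** An error-in-variables model needs a 2x2 error matrix for each comparison. A logistic fit and a Cox fit run separately give the two variances but not the covariance. If MRD is prognostic, as section 9.1.3 assumes, that covariance has the same sign as the association under study: an arm that by chance holds more MRD-positive patients looks worse on both scales. A regression that strips out both variances but treats the errors as independent would count this chance imbalance as trial-level association.

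R_T is the primary estimate, and the surrogate threshold effect rests on the same model. An upward bias would favour the study's hypothesis, and it need not be large to fill the 0.10 between 0.8 and 0.9. The earlier EFS/OS work fitted a joint patient-level model; section 9.1.4 names none for MRD and OS, so the step could seem to have been lost.

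**Working it through.** The protocol gives no figure for this covariance, so there is none to reproduce. Its power statement (above 85% at true R_T 0.9) cannot be rebuilt, because the number of comparisons is not given, and the point here does not depend on it.

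**Inputs.** From the documents: 1000 patients, null value 0.8, planning value 0.9, and 7 comparisons in 1,811 patients in the earlier EFS/OS work. Assumed: equal arms, 50% MRD-positive, 60% deaths, error correlation 0.3, and between-comparison SDs of log OR and log HR of 0.8/0.5 or 0.5/0.3.

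**Step 1: size if both variances are removed and the covariance is ignored.** With n patients per comparison, se_x = sqrt(4/(0.25n)) and se_y = sqrt(4/(0.6n)). The large-sample bias is 0.3 × se_x × se_y / (SD_x × SD_y), and it cannot exceed 1 − R_T.

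| n per comparison | se_x | se_y | Bias, SDs 0.8/0.5 | Bias, SDs 0.5/0.3 |
|---|---|---|---|---|
| 143 (1000/7) | 0.334 | 0.216 | +0.054 | +0.144 |
| 259 (1,811/7) | 0.249 | 0.160 | +0.030 | +0.080 |
| 500 | 0.179 | 0.115 | +0.015 | +0.041 |

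The cap is +0.20 at true 0.8 and +0.10 at true 0.9.

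**Step 2: is 0.3 a fair error correlation?** In 6000 simulated comparisons of 142 patients per scenario, with an MRD hazard ratio of 2 to 3, it was:
- 0.27 to 0.42 with MRD known in all patients;
- 0.21 to 0.33 with MRD known in a random 70%;
- 0.18 to 0.30 when the 30% without MRD had a poor prognosis.

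A separate simulation with 40% MRD-positive and hazard ratios from 1.5 to 3 gave 0.13 to 0.43. The sign is always positive and 0.3 is a fair middle value. The largest simulated covariance, 0.0311, gives 0.0311/0.15 = +0.21 before the cap.

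**Step 3: direction.** Take n = 143, true R_T 0.8 and the covariance ignored throughout. The error covariance is 0.3 × 0.334 × 0.216 = 0.0217. The observed covariance is then 0.8 × 0.40 + 0.0217 = 0.342 (SDs 0.8/0.5) or 0.8 × 0.15 + 0.0217 = 0.142 (SDs 0.5/0.3). Dividing by the SDs that each version of the regression would use:

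| Error variance removed | SDs 0.8/0.5 | SDs 0.5/0.3 |
|---|---|---|
| Both | 0.85 | 0.94 |
| Log OR only | 0.78 | 0.77 |
| Neither | 0.72 | 0.64 |

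Only the first row exceeds the truth.

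**Step 4: what modelling the covariance gains.** Results are for 7 units of 143 patients, error correlation 0.3, maximum likelihood and 1000 replicates per setting, shown as covariance set to zero against covariance modelled:

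| True R_T | SDs | Centre of estimate | Root mean square error |
|---|---|---|---|
| 0.6 | 0.8/0.5 | median 0.79 vs 0.70 | 0.43 vs 0.46 |
| 0.6 | 0.5/0.3 | median 1.00 vs 0.88 | 0.54 vs 0.62 |
| 0.8 | 0.8/0.5 | mean 0.86 vs 0.80 | 0.27 vs 0.32 |
| 0.8 | 0.5/0.3 | mean 0.87 vs 0.76 | 0.36 vs 0.48 |

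Modelling lowers the centre of the estimate but increases total error in all four settings. In the last, it undershoots by 0.04.

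**Step 5: the planned decision.** At true 0.8 with 7 units, a likelihood-ratio test rejected in 0 to 4.2% of runs with zero covariance and in 0 to 4.6% with it modelled. Both upper ends lie above 2.5%, but ignoring the covariance does not raise them.

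**The case for a change.** The strongest reply is that this bias is systematic, favours the hypothesis and does not shrink as comparisons are added. With 14 units of 143 at true 0.8, the mean is 0.86 against 0.80, or 0.92 against 0.81. With 70 units of about 142, the median is 0.86 to 1.00 against about 0.81. Specifying the error matrix would take a few lines and no new data, whereas settling it late leaves discretion over a confirmatory estimate.

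The statistical part stands: an analysis that removed both variances and assumed independent errors would overstate R_T, and with many comparisons this would matter. Two things limit its force. The many-unit settings need far more patients than the 1000 assumed (14 × 143 = 2,002 and 70 × 142 = 9,940). With 7 units, few comparisons dominate the error. The share of estimates above 0.8 at true 0.6 does rise (49% against 38%, and 70% against 56%), but section 9.1.3 does not declare surrogacy on a point estimate above 0.8; it tests the hypothesis.

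On discretion, the SAP must be final before database closure, and section 8 keeps the randomised arm out of the regular exports to the PERDAM database. Section 3.1.2 releases it only after each trial is unblinded. That narrows the room for choosing the error matrix to suit the result, though it does not close it, since participating trials may report their own results first.

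**Conclusion.** No change to the plan follows. This is a gap that analysts can be expected to fill sensibly. Section 9.1.4 commits to an error-in-variables model, individual patient data and a published meta-analytic approach, and the earlier EFS/OS work shows that the group has modelled endpoints jointly and allowed for estimation error. Whether reference [40] already supplies the covariance term cannot be checked from the documents. The concern therefore faults one possible way of running a step that the SAP has still to spell out.

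Under that one way, the large-sample overstatement is roughly 0.02 to 0.14 at an error correlation of 0.3, limited to 1 − R_T. Under the other two, R_T falls below the truth. The figures rest on assumed values for the number and size of comparisons, MRD rate, deaths, MRD hazard ratio and effect SDs, so the documents cannot place the study within that range. No harm to the planned 2.5% test, and no gain in accuracy from the correction, is shown with 7 comparisons.

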3.1.1 Study Alliance Leukemia (SAL) and Heidelberg Leukemia Network (HeLeNe) trials

Independently of the PERDAM trial, patients with either newly diagnosed or relapsed AML in the centers of the Study Alliance Leukemia (SAL) including the Heidelberg Leukemia Network (HeLeNe) are registered in the SAL-registry (NCT03188874) after informed consent is obtained. Samples including peripheral blood and bone marrow are sent to the reference labs

and analyzed for cyto- and molecular-genetics, immunophenotype and cryopreserved for biobanking. All patients with either newly diagnosed or relapsed AML are screened for eligibility for up-front randomized clinical trials. If patients are eligible and informed consent is obtained, patients may be included in these trials.

Currently, 2 studies are open for recruitment, the BLAST trial (ClinicalTrials.gov Identifiers: NCT02502968) and the DaunoDouble trial (ClinicalTrials.gov Identifier: NCT02140242). New studies may be added without need for an amendment of the PERDAM trial protocol.

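### The primary test of R_T ≤ 0.8 has no named statistic, confidence limit or boundary rule, and with about 1000 patients an ordinary plug-in limit on the error-corrected R_T would far exceed the 2.5% level

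*Combined protocol and SAP*

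**What the plan says.** Section 9.1.3 opens its hypothesis with "We aim to test the one-sided null hypothesis" and sets R_T ≤ 0.8 against R_T > 0.8 at 2.5%. On size it says "We assume that 1000 patients are eligible for MRD assessment by MPFC after induction/salvage therapy" and "The sample size of the proposed study is fixed by the limited number of randomized trials"; the number of trials or comparisons is not given. Section 3.1.1 says "Currently, 2 studies are open for recruitment" and allows more to join without an amendment. The power statement is "considering a true R_T of 0.9 the power to identify this effect will be larger than 85" per cent. In support, 9.1.3 cites an EFS-to-OS analysis with 7 comparisons and 1,811 patients (R = 0.99, lower 95% limit 0.85), and adds: "Based on this experience we also expect treatment effects in most of the trials being part of the application".

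Section 9.1.4 takes a log OR for MRD and a log HR for survival from each trial, fits an error-in-variables "regression model of the log transformed HRs on the log transformed ORs", and summarises the result by R_T². Neither section says how R_T is compared with 0.8, how a lower limit is formed, or what follows if the estimate reaches 1 or a variance is estimated as zero. Details are deferred to an SAP due before database closure.

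**The concern.** An error-in-variables fit takes the known sampling error out of the observed spread of log ORs and log HRs and forms R_T from what remains. If 1000 patients are divided over several comparisons, sampling error is about as large as a moderate spread of true effects. The corrected covariance matrix then often fails to be positive definite: R_T is truncated at 1, or a variance has no positive estimate. An R_T of 1 reads as perfect surrogacy although the data may say little.

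Usual limits break down there. Fisher's z is infinite at R = 1, and a delta-method Wald limit for R² has a variance proportional to R²(1 − R²)², which is zero at R = 1. Either counts a boundary fit as clear proof of R_T > 0.8. The false-positive rate of the only primary hypothesis therefore depends on a rule that the plan does not state.

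The argument from expected treatment effects does not supply what is needed. R_T is identified by differences in effect between comparisons; a similar benefit in every trial carries almost no information about it.

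**Working it through.** **1. The plan's power figure.** Take the comparison as the unit and ignore estimation error, which is the best case. With K comparisons, power = Φ((atanh 0.9 − atanh 0.8)·√(K − 3) − 1.96), where atanh 0.9 − atanh 0.8 = 1.472 − 1.099 = 0.374.
- K = 7: Φ(0.374 × 2 − 1.96) = Φ(−1.21) = 11%.
- K = 10, 20 and 40: 17%, 34% and 62%.
- 85% is first reached at K = 68, about 1000/68 ≈ 15 patients per comparison.

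The stated figure is not reproduced. Only treating the 1000 patients as the units gives power near 100%.

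**2. Inputs.** From the documents: about 1000 patients, null value 0.8, 2.5% one-sided, the error-in-variables model, and 7 comparisons in the cited precedent. Assumed, because not stated: equal comparisons, 50% MRD-positive, 55% deaths, independent errors and the between-trial SDs. A second simulation assumed 40% positive, 50% deaths and error correlation 0.3.

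**3. Sampling error at K = 7**, n = 1000/7 = 143 per comparison:
- Var(log OR) = 16/143 = 0.112, SE 0.33.
- Var(log HR) = 4/(0.55 × 143) = 0.051, SE 0.23.
- With true SDs 0.40 and 0.25, the reliability ratios are 0.16/(0.16 + 0.112) = 0.59 and 0.0625/(0.0625 + 0.051) = 0.55.

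For scale, one SD of 0.40 and 0.25 is a factor of e^0.40 = 1.5 in the OR and e^0.25 = 1.3 in the HR. SDs of 1.2 and 0.6 are factors of 3.3 and 1.8.

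**4. How often there is no interior estimate.** Trial effects were simulated with the true covariance plus sampling error, and the error covariance was subtracted. At K = 7, SDs 0.40/0.25 and true R_T = 0.8, R_T was 0.99 or more in 38% of runs and a variance was non-positive in a further 26%: about 64%. At true R_T = 0.5 the shares were 24% and 26%.

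Under the second set of assumptions, the share of runs at the boundary or with a non-positive variance was:

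| SDs (log OR / log HR) | true R_T = 0.8, K = 7 | true R_T = 0.8, K = 4–40 | true R_T = 0.5, K = 4–40 |
|---|---|---|---|
| 0.3 / 0.15 | 78% | 77–84% | 72–80% |
| 0.5 / 0.25 | 59% | 57–69% | 44–60% |
| 0.8 / 0.4 | 34% | 30–48% | 13–36% |

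At SDs 1.2/0.6 the share at true R_T = 0.8 is about 20%.

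**5. Rejection rate at true R_T = 0.8 (nominal 2.5%), 1000 patients, K = 4–20, SDs 0.30/0.15 to 1.2/0.6.** A non-positive variance never counts as rejection.
- Fisher z on the corrected R_T, R_T = 1 counted as success: 19–45% (base case 39–40%).
- Delta-method Wald limit on R_T², same rule: about 42% in the base case. Fisher z and Wald together span about 19–47%.
- Fisher z, R_T = 1 counted as failure: 0.1–17% (about 2% in the base case).
- At the extreme SDs 2.0/1.0 and K = 7, Fisher z with R_T = 1 as success still rejects 10%.

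In the base case with true R_T = 0.5, Fisher z with R_T = 1 as success declares R_T > 0.8 in about 25% of runs.

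**6. A test that does not use the point estimate.** A profile likelihood-ratio test with the ordinary critical value rejected 0–2.2% at true R_T = 0.8 over the grid in step 4, up to 4.3% in a sensitivity grid at K = 7, and 2.5–9.5% at very large spread. Its power at true R_T = 0.9 over the step 4 grid was 0–4.2%.

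**The case against.** The plan names neither Fisher z nor a Wald limit, and it does not say that R_T = 1 counts as success. An SAP is still to come, and a likelihood-ratio test on the same trial-level model stays near or below its level in most settings. This stands. A reader might infer that no test built on this estimator can hold 2.5%, or that the trial's own test is known to be inflated. The documents support neither reading: the inflation belongs to particular tests, and the plan has not chosen one.

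A reader might also infer that R_T will land at 1 whatever its true value. That goes too far. The frequency depends on a between-trial spread that the documents do not state, and boundary fits become a minority when the spread is large.

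The remark about expected effects follows a report of substantial effects in 4 of 7 earlier comparisons. Effects in some comparisons and not in others are a form of spread, so the remark is not empty; but it is not quantified.

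The 1000 is a minimum. More patients help slowly: at K = 7 and SDs 0.5/0.25, boundary or non-positive-variance fits at true R_T = 0.8 are 43% with 1,811 patients and 30% with 3,000, and Fisher z with R_T = 1 as success rejects 38% and 32%.

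Deferral to the SAP does not settle the matter. The hypothesis, level and estimator are already fixed, and the boundary rule decides the result. It should be set before any trial-level effects are seen.

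**Conclusion.** The concern holds in this form: the level of the primary test is not secured, because the plan fixes the estimator and the error rate but not the test, the limit or the boundary rule. With about 1000 patients, boundary or zero-variance fits are common, and they are the majority when the spread of true effects is small or moderate. The most familiar way to complete the plan would raise the false-positive rate from 2.5% to about 19–47%; treating R_T = 1 as failure does not reliably repair it. The percentages rest on assumed MRD-positive rates, death fractions, numbers of comparisons and between-trial SDs; they show a range and do not predict this study's result. The stated power above 85% is not supported under any plausible number of comparisons examined.

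**What to change.** In sections 9.1.3 and 9.1.4, and carried into the SAP:

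1. Fit the bivariate random-effects model with the estimated within-trial error covariance. Test R_T ≤ 0.8 by profile likelihood ratio, with the critical value calibrated by parametric bootstrap under R_T = 0.8. Calibration is needed because the ordinary critical value was too liberal at very large spread.
2. State in advance that a point estimate of R_T = 1, or a zero variance estimate, is not by itself evidence of surrogacy. Claim success only if the calibrated lower limit exceeds 0.8. Automatic failure at R_T = 1 is not proposed, since it would also block a nearly perfect surrogate.
3. Report both reliability ratios and leave-one-comparison-out predictions of the log HR beside R_T.
4. Replace the argument from expected treatment effects with the number of comparisons and the between-trial spread that the design needs, with simulated level and power over a stated range.

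The cost is SAP wording, a standard likelihood fit and a simulation; no new data are needed. The drawback should be stated openly: a test that keeps its level had only about 0–4% power at true R_T = 0.9 in the settings examined, so the power statement has to be rewritten and a positive primary result becomes much less likely.
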